2.1 Minimized risks to participants

45 CFR 46.111 (a) 1 and 21 CFR 56.111 (a) 1: Risks to subjects are minimized.

This protocol minimizes risks to participants by (a) correctly and promptly informing participants about risks so that they can join in partnership with the researcher in recognizing and reporting harms; (b) respecting local/national blood draw limits; (c) performing direct observation of participants postvaccination and collecting information regarding side effects for several days postvaccination; (d) having staff properly trained in administering study procedures that may cause physical harm or psychological distress, such as blood draws, vaccinations, HIV testing and counseling and HIV risk reduction counseling; (e) providing HIV risk reduction counseling and checking on contraception use (for persons assigned female at birth); and (f) providing safety monitoring.

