The protocol was amended and participants in Groups 1 and 2 were given the option to receive a third dose for 3 total doses. Nine (out of 17) participants elected to receive a third dose. There were no unsolicited Grade-3 or -4 AEs and no related SAEs, AESIs, or deaths in either group after this third dose. Both local and systemic reactogenicity were similar between all 3 doses in participants who received 3 doses in Part A.

HVTN 137 Part B is evaluating the safety and immunogenicity of 100-mcg BG505 SOSIP.664 gp140 in combination with 3 TLR agonists, including 5-mcg 3M-052 AF + 500-mcg Alum, and Alum alone. Enrollment is now complete and 88 participants have been enrolled. Of these 88 participants, 20 have been randomized to the 3M-052-AF + Alum group. All 88 participants have received at least two doses and, as of June 7th, 81 have received the third dose. Given that the

trial remains blinded across the 4 treatment arms, interpretation of the blinded safety data from HVTN 137 Part B is not possible, but there have been no related SAEs, AESIs, deaths, or unplanned study pauses. No additional grade 3 local reactogenicity events have been observed.

Overall, BG505 SOSIP.664 with 3M-052-AF + Alum was generally well tolerated, with no unsolicited Grade-3 or -4 AEs; no related SAEs, AESIs, or deaths; and no unplanned study pauses. Other than the persistent erythema in one of the HVTN 137 Part A Group 2 participants described above, all reactogenicity symptoms resolved within 14 days and generally within 7 days. For more detailed information, please see the IB.

HVTN 300 (NCT04915768): Refer to Section 4.5.3 for more information.

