7.4.1 Delaying vaccinations for a participant

Under certain circumstances, a participant's scheduled vaccination will be delayed. The factors to be considered in such a decision include but are not limited to the following:

- Within 45 days prior to any study injection
 - Receipt of blood products or immunoglobulin
- Within 30 days prior to any study injection
 - Receipt of live attenuated vaccines
 - Receipt of allergy treatment with antigen injections
 - Receipt of ACAM2000 vaccine for monkeypox
 - After administration of ACAM2000 vaccine, a minimum of 30 days is required before administration of study vaccination if vaccination scab no longer present,
 - If a vaccination scab still present 30 days after receiving ACAM2000, delay study vaccination until the scab is no longer present;
- Within 14 days prior to any study injection
 - Receipt of any vaccines that are not live attenuated vaccines (eg, pneumococcal); replication incompetent vaccines such as the Jynneos monkeypox vaccine are not considered to be live vaccines

• Prevaccination abnormal vital signs or clinical symptoms that may mask assessment of vaccine reaction.

Vaccinations should not be administered outside the visit window period (see Appendix W).

In order to avoid vaccination delays and missed vaccinations, participants who plan to receive licensed vaccines or allergy treatments should be counseled to schedule receipt of these substances, when possible, outside the intervals indicated above. The effects of these substances on safety and immunogenicity assessments and their interactions with study vaccines are unknown. Therefore, if circumstances allow, these substances should also be avoided in the interval between a study vaccination and completion of the 2 or 3-week postvaccination follow-up visit.

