10.1 HVTN CRS laboratory procedures

The HVTN 137 Site Lab Instructions and SSP provide further guidelines for operational issues concerning the clinical and processing laboratories. These documents include guidelines for general specimen collection, special considerations for phlebotomy, specimen labeling, whole blood processing, HIV screening/diagnostic testing, and general screening and safety testing.

Tube types for blood collection are specified in Appendix J, Appendix K, Appendix L, Appendix M, Appendix N, Appendix O, and Appendix P. For tests performed locally, the local lab may assign appropriate tube types.

In specific situations, the blood collection tubes may be redirected to another laboratory or may require study-specific processing techniques. In these cases, laboratory special instructions will be posted on the protocol-specific section of the HVTN website.

Of note, all assays described below are performed as research assays to evaluate the ability of the vaccine to induce immune responses in the context of the participants' genetic background and are not approved for use in medical care. Results from these assays are not made available to participants or medical professionals to guide treatment decisions.

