10.2 Total blood volume

Required blood volumes per visit are shown in Appendix J, Appendix K, Appendix L, Appendix M, Appendix N, Appendix O, and Appendix P. Not shown is any additional blood volume that would be required if a safety lab needs to be repeated, or if a serum pregnancy test needs to be performed. The additional blood volume would likely be minimal. The total blood volume drawn for each participant will not exceed 500 mL in any 56-day (8-week) period.

The preferred laboratory specimen tube types for research samples are shown in Appendix J, Appendix K, Appendix L, Appendix M, Appendix N, Appendix O, and Appendix P. Alternate tube types may be used under certain circumstances (eg, ACD tube shortages) upon approval of the HVTN Laboratory Center. Refer to the HVTN 137 Specimen Collection SSP for more information.

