- Item 1 Removed in *Section 6.2, Randomization*: stratified randomization and requirement for at least half of the participants in Part B to consent to the fine needle aspiration procedure
- Item 2 Removed in Laboratory Procedure Tables for Part B (Appendices I, J, K, and L): Prothrombin time / INR testing
- Item 3 Corrected in Appendix B, SICF for Part B, item 15: participant instructions for rectal tissue collection
- Item 4 Updated in Section 3.1, *Protocol team*: Membership
- Item 5 Corrected a document error in Protocol Version 2, Letter of Amendment 2, dated July 16, 2020: upper allowable visit window for the Final Visit (Visit 14.0) in Part A

Date: July 16, 2020

Protocol version: Version 2.0

Protocol modification: Letter of Amendment 2

Item 1 Updated *Appendix S* Visits Windows to expand the upper allowable window for Visit 7/Vaccination 2 from 120 days to 180 days

Date: June 11, 2020

Protocol version: Version 2.0

Protocol modification: Letter of Amendment 1

- Item 1 Updated with changes described in Protocol Version 2, Clarification Memo 3, dated March 24, 2020
- Item 2 Updated in Section 3.1, Protocol team: Membership

Date: March 24, 2020

Protocol version: Version 2.0

Protocol modification: Clarification Memo 3

Item 1 Clarified in Appendix S, Visit windows: Allowable visit windows for Part A

Item 2 Clarified throughout protocol: "Clinic visits"

Date: January 27, 2020

Protocol version: Version 2.0

Protocol modification: Clarification Memo 2

Item 1 Reconciled in Section 7.2, *Exclusion criteria*: Exclusion for autoimmune conditions

Date: December 12, 2019

Protocol version: Version 2.0

Protocol modification: Clarification Memo 1

- Item 1 Clarified in Section 6.3, *Blinding*: Treatment assignment but not group assignment blinded throughout trial
- Item 2 Clarified in Inclusion criterion 23 in Section 7.1: No alternative pregnancy methods until 6 months after last vaccination
- Item 3 Clarified in Appendices H through M: Lab procedures table footnotes regarding optional blood draws and blood draw totals
- Item 4 Corrected in Section 13: Version history

Date: October 30, 2019

Protocol version: Version 2.0

Protocol modification: Full Protocol Amendment 1

- Item 1 IND number added to title page
- Item 2 Age eligibility clarified
- Item 3 SAE and MAAE reporting added throughout protocol duration
- Item 4 Safety experience of CpG 1018 revised in Section 4.5.1 and Appendix B

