⁸ At an early termination visit for a withdrawn or terminated participant who is not HIV-infected (see Section 9.12), blood should be drawn for HIV diagnostic testing, as shown for visit 16 above. If a participant has a confirmed diagnosis of HIV infection, do not collect blood for HIV diagnostic testing (see Section 9.14).

⁹ Fc-mediated Ab functions may include FcR binding assay, ADCC, ADNP ADCP, and complement assay.

¹⁰ The 56-day total blood volume does not include up to 16.5 mL blood collected for a reaction (see Section 9.10.1); however, the 56-day limit is not exceeded at any visit by this possible collection.

¹¹ Specimens indicated for Day 0 may be obtained within the 14 days prior to vaccination, except for a pregnancy test which must be performed on urine or blood specimens within 24 hours of vaccination with negative results received prior to vaccination.

¹² Antibody avidity, peptide microarray, metabolomic profiles, and proteomics assays may be done with serum collected for storage.

y = SST blood collected for the Binding Ab and Neutralizing Ab assays will also cover specimen needs for the Fc-mediated Ab function assays; no separate blood draw is needed.

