**HVTN 137 Part B and Part C Visit Windows** 

Visit Number	Visit Type	Lower Allowable Window (-)	Lower Target Window (-)	Target Day ¹	Upper Target Window (+)	Upper Allowable Window (+)
01.0	Screening	-56	-	0	-	+0
02.0	Enrollment/Vaccination 1	-	-	0	-	-
03.0	1 day postvaccination 1	-0	-	1	-	+0
04.0	3 days postvaccination 1	-0	-	3	-	+0
05.0	7 days postvaccination 1	-1	-	7	-	+1
06.0	2 weeks postvaccination 1	-	-4	14	+4	+7
07.0	Vaccination 2	-	-7	56	+9	+14
08.0	7 days postvaccination 2	-1	-	63	-	+1
09.0	2 weeks postvaccination 2  Primary Immunogenicity	-	-4	70	+1	+4
10.0 ²	FNA visit	-3	-1	77	+4	+7
11.0	Vaccination 3	-	-7	168	+9	+14
12.0	7 days postvaccination 3	-1	-	175	-	+1
13.0	2 weeks postvaccination 3  Primary Immunogenicity	-	-4	182	+4	+7
14.0 ³						
15.0	Follow-up Visit	-84	-14	364	+14	+84
16.0	Final Visit	-56	-14	546	+14	+28

¹ All target dates are relative to Day 0, with the exception of the postvaccination visits, visits 8.0, 9.0, 10.0, 12.0, and 13.0, which are relative to the vaccination immediately preceding the visit.

 $^{^{2}}$  The green highlighted visit is only required for participants who are providing lymph node FNA collections in Part B.

³ The highlighted (blue) visit is not required for any Part B or Part C participants.

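### Part C: visits kept inside the Appendix W windows can draw 551.5 or 559 mL in 56 days, against a stated cap of 500 mL

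*Protocol*

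**What the plan says.** Section 10.2 (Total blood volume) sets the cap with no exception: "The total blood volume drawn for each participant will not exceed 500 mL in any 56-day (8-week) period". Section 2.1 counts "respecting local/national blood draw limits" among the ways risk to participants is kept down.

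Appendix P gives the Part C draws, with a running 56-day total at each visit. The highest is 478 mL, at Visit 7. Its footnote 10 says these totals leave out up to 16.5 mL taken for a reaction and adds: "however, the 56-day limit is not exceeded at any visit by this possible collection".

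The Part B and Part C table in Appendix W sets the windows. Its footnote 1 fixes the anchors: "All target dates are relative to Day 0, with the exception of the postvaccination visits, visits 8.0, 9.0, 10.0, 12.0, and 13.0". Those five visits count from the preceding vaccination and the rest from Day 0. Section 7.4.1 makes the vaccination window binding: "Vaccinations should not be administered outside the visit window period (see Appendix W)".

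Section 10.1 leaves operational matters, including "special considerations for phlebotomy", to the Site Lab Instructions and the Study Specific Procedures (SSP), which are not available here.

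**The concern.** The cap is absolute and footnote 10 reassures sites that it holds, but the totals behind both are target-day totals. Giving Vaccination 2 early pulls Visit 8 (93.5 mL) and Visit 9 (227 mL) toward the first-week draws, which do not move. A site could follow Appendix W exactly, rely on footnote 10, and draw more blood than the protocol promises.

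What is at stake is a participant protection. No endpoint or group comparison is affected. Part B is past this stage, since Section 4.5 reports that "All 88 participants have received at least two doses". The live exposure is Part C, about 127 − 17 − 88 = 22 people.

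**Working it through.** **Inputs: volumes.** Unrounded sums of the Appendix P tube rows, in mL:

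| Visit | 1 | 2 | 3 | 4 | 5 | 6 | 7 | 8 | 9 |
|---|---|---|---|---|---|---|---|---|---|
| mL | 20 | 169.5 | 25 | 25 | 84.5 | 137.5 | 16.5 | 93.5 | 227 |

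**Inputs: windows.** From Appendix W, Part B and Part C:

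- Visits 2, 3 and 4: Days 0, 1 and 3
- Visit 5: Days 6–8
- Visit 6: Days 10–21
- Visit 7 (Vaccination 2): Days 49–70
- Visit 8: Visit 7 + 6 to 8 days
- Visit 9: Visit 7 + 10 to 18 days

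**Reproducing the printed totals.** On target days, summing draws up to 56 days apart gives 478 at Visit 7 (Visits 1–7), 332 at Visit 8 (Visits 5–8) and 474.5 at Visit 9 (Visits 6–9, printed as 475). All match. With the reaction draw, 478 + 16.5 = 494.5 mL, so footnote 10 is right on target days. The Visit 8 total also shows how the table counts: 332 is Visits 5–8, so Day 7 and Day 63 are both included, which is 57 calendar days. Two counts are therefore used below:

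- *Strict:* draws at most 55 days apart (56 calendar days)
- *Table's:* draws at most 56 days apart

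**Sums that can exceed the cap.**

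- Visits 2–8: 169.5 + 25 + 25 + 84.5 + 137.5 + 16.5 + 93.5 = **551.5 mL** (571.5 if screening blood is drawn on Day 0)
- Visits 5–9: 84.5 + 137.5 + 16.5 + 93.5 + 227 = **559 mL**
- Visits 4–9: 25 + 559 = **584 mL**

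**When they fall within 56 days, strict count.**

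- Visits 2–8 need Visit 8 by Day 55, so only Vaccination 2 on Day 49 with Visit 8 six days later.
- Visits 5–9 need Visit 9 at most 55 days after Visit 5, which is possible for Vaccination 2 on Days 49–53. The latest case is Visit 5 on Day 8, Vaccination 2 on Day 53 and Visit 9 on Day 63.

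**Table's count.** Visits 2–8 can breach for Vaccination 2 on Days 49–50 and Visits 5–9 on Days 49–54. Visits 4–9 (584 mL) breach for Vaccination 2 on Day 49 with Visit 9 on Day 59.

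**Example inside the target windows.** Visit 5 on Day 7, Vaccination 2 on Day 49 and Visit 9 on Day 59 give 559 mL over 59 − 7 + 1 = 53 calendar days. This is a breach on either count.

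**Full enumeration.** There are 3 × 12 × 22 × 3 × 9 = 21,384 in-window combinations of Visit 5–9 days, 972 for each Vaccination 2 day. Those over 500 mL:

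| Vaccination 2 day | 49 | 50 | 51 | 52 | 53 | 54 | 55+ | Total |
|---|---|---|---|---|---|---|---|---|
| Strict | 612 | 324 | 216 | 108 | 36 | 0 | 0 | 1,296 (6.1%) |
| Table's | 828 | 612 | 324 | 216 | 108 | 36 | 0 | 2,124 (9.9%) |

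These are shares of combinations, not probabilities, and they place the whole Visit 2 draw on Day 0.

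**Is a breach ever forced?** No. Every choice of Visit 5, 6 and 7 days leaves a compliant Visit 8/9 pair. The tightest case is Vaccination 2 on Day 49, where 8 to 12 of the 27 pairs comply (strict) or 3 to 5 of 27 (table's count).

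**The case against.** The strongest reply is that the cap and the windows bind together. A site that picks an over-cap day breaks Section 10.2, whatever Appendix W allows, and since a compliant Visit 8/9 pair always exists, both can be met. Every printed volume and total is correct, and footnote 10 can be read as describing the target-day table. Scheduling instructions may sit in the SSP or Site Lab Instructions. On this view the protocol lacks a reminder and contradicts nothing.

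Much of this stands. No breach is forced, and the unseen documents may cover the point. Early vaccination alone is not enough on the strict count: with the other visits on target timing, Vaccination 2 on Days 49–56 gives at most 474.5 mL. On the table's count, only Day 49 then breaches (559 mL, or 571.5 mL with screening).

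Appendix P footnote 11 also lets Day 0 specimens be drawn up to 14 days earlier. Moving that draw two days earlier removes the 551.5 mL case and cuts the over-cap combinations to 1,116 (strict) or 1,656 (table's count). It does nothing for the 559 mL case, which starts at Visit 5.

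What does not stand is the assurance itself. Footnote 10 says the limit is not exceeded at any visit, and for some in-window schedules it is. The protocol text gives a site no cue that Vaccination 2 on Day 49 calls for care in placing Visits 8 and 9.

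**Conclusion.** The point holds and is minor. For Part C, the Appendix W windows do not guarantee the Section 10.2 cap. In-window schedules can reach 559 mL (59 mL over) for Vaccination 2 on Days 49–53, and 551.5 mL (51.5 mL over) for Vaccination 2 on Day 49 with Visit 8 on Day 55, both on a strict 56-day count. On the table's own count the range extends to Day 54 and the maximum is 584 mL.

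This rests on the Appendix P volumes being drawn in full. The 551.5 mL case also needs the Visit 2 samples taken on Day 0. Repeat safety tests and reaction draws would only add volume. How often the pattern would occur cannot be judged from the protocol.

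**What to change.** Add one rule for Part C to Appendix W and Appendix P: when Vaccination 2 is given before Day 55, schedule Visit 8 on or after Day 57 and Visit 9 at least 57 days after Visit 5. This fits the current windows for every permitted Vaccination 2 day. For Day 49 it means Visit 8 on Day 57, and Visit 9 from Day 63, 64 or 65 (for Visit 5 on Day 6, 7 or 8) to Day 67. Reword footnote 10 so that it applies to target-day scheduling, and notify Part C sites.

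The rule removes exactly the 2,124 combinations over 500 mL on the table's count and leaves 19,260. Among these the maximum is 478 mL including screening, or 494.5 mL with one reaction draw. No tube is dropped and the vaccination window is unchanged.

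There is some cost in timing. Of the combinations removed, 2,124 − 1,296 = 828 comply on the strict count. With Vaccination 2 on Day 49, Visit 8 moves to 8 days after vaccination instead of 7. If Visit 5 was on Day 8, Visit 9 falls at least 16 days after vaccination, past its upper target of 15 but inside the allowable 18.

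A heavier alternative is to change the lower window for Vaccination 2 from −7 to −1 days. That cuts the window from 22 to 16 days and makes it differ from Part B. The version history (Section 13) shows a window change made by Letter of Amendment, to "expand the upper allowable window for Visit 7/Vaccination 2 from 120 days to 180 days". The 180-day limit now appears only in the Part A tables, so this is a precedent for the route only.

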10.3 Primary immunogenicity timepoint

The primary immunogenicity timepoints in this study occur 2 weeks after the last vaccination for groups receiving 2 vaccinations and 1 and 2 weeks after the second and third vaccinations for the groups receiving 3 vaccinations. For the

group receiving 3 vaccinations, primary timepoints for innate immunity and inflammation assays are baseline, and days 1, 3, and 7 post first vaccination.

Endpoint assays for humoral and cellular responses are performed on specimens collected from participants at the primary immunogenicity timepoint and may be performed on samples collected at baseline. Depending on the initial results, assays for humoral, cellular, innate immunity, and inflammatory responses may be performed on samples collected from participants at other timepoints; the schedules are shown in Appendix J, Appendix K, Appendix L, Appendix M, Appendix N, Appendix O, and Appendix P.

10.4 Endpoint assays: cellular

10.4.1 Intracellular cytokine staining (ICS) assay

Flow cytometry will be used to examine vaccine-specific CD4+ T-cell responses following stimulation of PBMCs with synthetic HIV peptides that span the HIV-1 envelope protein. ICS parameters will include cytokines such as interferon gamma (IFN- γ), interleukin (IL)-2, and TNF- α , and may include other cytokines (such as cytokines relevant to Th2 and Th17 responses) to identify T cells of specific functionality. Data will be reported as percentages of CD4+ T cells responding to a specific peptide pool. Additional cell surface markers, cytokines, or functional markers may also be analyzed.

10.4.2 CD4+ T follicular helper cells (Tfh/pTfh)

Multicolor flow cytometry may be used to identify, phenotype and isolate circulating CD3+ T cells in the peripheral blood (PBMC) and LN FNAs. Peripheral Tfh may be characterized based on expression of lineage markers including CXCR5, PD-1, and ICOS on CD4+ T cells. Functionality of Tfh cells might be tested by in vitro stimulation of cells with synthetic HIV peptides that span the HIV-1 envelope protein to identify, enumerate and immunophenotype antigen-specific Tfh cells.

10.4.3 Env-specific B cell and plasmablast phenotyping

HIV-1 Env-specific B cells and plasmablasts induced by vaccination will be identified and characterized using fluorescently-labeled recombinant Env proteins (including BG505 SOSIP.664) in combination with a flow cytometry antibody panel. In particular, Env-reactive B cells and plasmablasts will be enumerated and may be further characterized for expression of memory, activation, inhibitory or other markers of interest.

10.4.4 BCR repertoire analysis

Single or bulk populations of memory B cells and plasmablasts may be sorted for BCR sequencing and gene expression analysis. Env-specific B cells may instead

be expanded for detection of and functional testing of secreted antibodies by enzyme-linked immunosorbent assay (ELISA) or microneutralization assays, and BCR sequencing. The resulting VH and VL genes may be cloned into an IgG backbone for antibody expression and characterization of the binding, epitope-specificity, and neutralization.

10.4.5 Epitope Mapping

Epitope mapping will be performed using either the ICS or IFN-γ ELISpot assays. PBMCs will be stimulated with synthetic peptides that span the BG505 SOSIP.664 gp140. Epitope mapping will be performed using BG505 SOSIP.664 gp140 15-mer peptides overlapping by 11 aa. Once positive responders are identified using peptide pools, the specific responses will be mapped to the single 15 amino acid peptides.

10.5 Endpoint assays: humoral

10.5.1 Binding antibody multiplex assay (BAMA)

HIV-1—specific total binding IgG antibodies will be assessed on serum samples from study participants taken at the primary immunogenicity timepoints and baseline. In addition, HIV-1—specific total binding IgA antibodies and binding to IgG subclasses (IgG1, IgG2, IgG3, and IgG4) may also be assessed. Specimens from other timepoints may also be assayed based on the results of the initial assay.

10.5.2 Antibody avidity

Antibody avidity may be measured using BAMA with the addition of a dissociation step to calculate the antibody avidity index (BAMA-AI). Biolayer Interferometry (BLI) and/or Surface Plasmon Resonance (SPR) technologies may also be used to define antibody avidity.

